5. HYPOTESIS

The assumptions leading to the start of this study are as follows:

5.1 Main hypothesis:

Using **pressure support ventilation** for the weaning in extremely and very preterm neonates with newborn respiratory distress syndrome on invasive mechanical ventilation, reduces the number of reintubations, in comparison with the use of **assist control volume guarantee ventilation**.

5.2 Secondary hypothesis:

Using **pressure support ventilation** for the weaning in extremely and very preterm neonates with newborn respiratory distress syndrome on invasive mechanical ventilation, reduces the time of weaning, in comparison with the use of **assist control volume guarantee ventilation**.

6. OBJECTIVE

The proposed project has the following objectives:

6.1 Main objective:

To compare the number of reintubations of **pressure support ventilation** and **assist control volume guarantee ventilation** when used for weaning, in extremely and very preterm neonates with newborn respiratory distress syndrome on invasive mechanical ventilation.

6.2 Secondary objectives:

To compare the time of weaning of **pressure support ventilation** and **assist control volume guarantee ventilation** when used for weaning, in extremely and very preterm neonates with newborn respiratory distress syndrome on invasive mechanical ventilation.

7. SUBJECTS AND METHODS

7.1 Study design

This project is designed as a **multicentre clinical trial** to compare two different modalities of weaning (PSV and ACVGV) in extremely and very preterm newborns with NRDS. As it will be multicentric, it will be conducted in 5 different centres over Catalonia.

A **consecutive stratified sampling** will be done, participants will be selected when they are on invasive mechanical ventilation due to NRDS and meet the inclusion criteria. The two groups will be created by **randomization** in a ratio 1:1, so that there is **equivalence** between them.

Regarding the masking method, it will be **simple blinded**, as the preterm newborns will not know which protocol they are assigned to.

7.2 Study population

Inclusion criteria

- Preterm neonate, born at less than 32 weeks of gestation.
- Must be on invasive mechanical ventilation due to neonatal respiratory distress syndrome.
- Informed consent signed by parent or legal guardian.

Exclusion criteria

- Any congenital malformations
- Any chromosomopathies
- Any cardiopathies
- Any neurological malformations

These criteria have been selected because all of these pathologies can affect the patient's respiratory pattern, so it is possible that newborns with these criteria may have different management necessities, more time on mechanical ventilation, or more complications related to their underlying pathology.

Withdrawal criteria

- **Request to revoke consent for the study:** the parents or legal guardians of the neonate can express voluntary decision to be excluded from the study at any point. (see Annex 6)
- **Neonates' death:** from enrolment until the end of the follow-up period.

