3.2.9 Prognosis

The prognosis for infants managed with antenatal steroids, respiratory support, and exogenous surfactant therapy is excellent. Mortality is less than 10%, with some studies showing survival rates of up to 98% with advanced care.

The improved survival in developed countries contrasts sharply with babies who received no intervention in low-income countries, where the mortality rate for premature infants with RDS is significantly higher, sometimes approaching 100%.(48)

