7.3 Sampling

7.3.1 Sample size

We estimated the sample size using the free online software GRANMO, and the setting for two independent proportions.

In the view of the literature published so far, the proportion of reintubation in preterm newborns that are on invasive mechanical ventilation is 16% (studies differ between 12% and 20%, an average has been made).(62,63)

Accepting an alpha risk of 0.05 and a beta risk of 0.2 in a two-sided test, **271** subjects are necessary in first group and **271** in the second to recognize as statistically significant a difference greater than or equal to 0.1 percent units. A proportion in one of both groups has been estimated to be 16%. It has been anticipated a drop-out rate of 5% (0,05).

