- 6. Formation sessions** (April 2024): An online meeting will be held with the whole team to provide theoretical training on neonatal resuscitation and neonatal mechanical ventilation. Particular emphasis will be placed on invasive mechanical ventilation and weaning. During this meeting, a consensual and detailed document will be sent to the hospital coordinators of each centre with the values of each parameter of the ventilator necessary for both the initiation of weaning and extubation. It will also include the clinical and gasometrical criteria for weaning, extubation and reintubation.

The aim of this training is to homogenise the process and reduce differences in the results between centres.

- 7. Creation of a database** (April 2024): A computer scientist will be hired to create a database, so that the data collected before, during and after the intervention can be correctly recorded.

STAGE 3: Sample recruitment, intervention, and data collection (27 months: May 2024 – July 2026)

8. Sample recruitment: As mentioned above, a consecutive stratified sampling method of extremely and very preterm newborns with NRDS that are on invasive mechanical ventilation, admitted to the NCIU of the participating hospitals will be carried out. Each co-investigator at each centre will be responsible for enrolling patients who meet all the inclusion criteria and any of the exclusion criteria, after the parents or legal guardians have signed the informed consent form (see Annex 5). Each participant will be randomised to one of the intervention groups of the clinical trial. The hospital coordinators of each centre will supervise this process.

Recruitment will continue until each centre has recruited the number of participants assigned by the stratification, with a 1:1 ratio. This is expected to take approximately 26 months (2 years and 2 months).

9. Intervention: During this period, patients will be assigned to one of the protocols for weaning, PSV in one arm of the study and ACVGV in the other.

This process can take a few days or even a few weeks, so an extra month has been added to the projected 26 months for this stage.

10. Follow up: After the intervention, all patients enrolled in the study will be followed for the first 72 hours after extubation, as all clinical data will be recorded in the baby's medical record.

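### Death is a withdrawal criterion up to 72 h after extubation, and the plan has no rule for analysing or recording infants who die after randomisation

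*Combined protocol and SAP*

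**What the plan says.** Section 7.2 gives two withdrawal criteria. One is revoked consent: parents or guardians "can express voluntary decision to be excluded from the study at any point". The other is the infant's death, "from enrolment until the end of the follow-up period".

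Sections 7.5 and 10.3 place enrolment while the infant is ventilated, randomisation at the start of weaning, and the end of follow-up at 72 h after extubation. Section 7.4 counts reintubations over those 72 h and measures weaning time from the start of weaning to extubation. Section 7.7 (Period 3) has reintubation assessed once the 72 h have passed.

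Section 8 plans a t-test and Poisson regression for reintubations, and Kaplan-Meier and Cox analyses for weaning time. It defines no analysis population, no missing-data rule and no handling of death. Death is not an outcome or covariate in section 7.4 or Table 4. The intervention block of the Annex 7 form holds only the protocol code, reintubation and weaning time in days.

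The only allowance for losses is in section 7.3.1: "It has been anticipated a drop-out rate of 5% (0,05"). Section 3.2.9 says of treated disease in general: "Mortality is less than 10%, with some studies showing survival rates of up to 98% with advanced care".

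**The concern.** Death after randomisation prevents or cuts short both outcomes, and the assigned weaning mode may influence it. If withdrawal means leaving the analysis, the groups compared are no longer the groups that were randomised. An infant who is reintubated and then dies within 72 h may take a genuine primary event out of the data. An infant who dies before extubation has no weaning time under the section 7.4 definition.

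Because the rule is unwritten, someone would have to choose how to treat these infants after the data exist. The data form would not show the statistician who had died. At stake are an unbiased comparison of the two modes and any account of mortality by arm.

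**Working it through.** **1. The plan's own figure.** Section 7.3.1 sets "Accepting an alpha risk of 0.05 and a beta risk of 0.2 in a two-sided test". The reference value is "A proportion in one of both groups has been estimated to be 16" per cent, and the aim is "to recognize as statistically significant a difference greater than or equal to 0.1 percent units". I read the last as 0.10, that is, 10 percentage points. The unpooled normal formula for 16% versus 26% gives

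n = (1.960 + 0.842)² × (0.16×0.84 + 0.26×0.74) / 0.10² = 256.5, so 257 per arm.

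257 / 0.95 = 270.5, so 271. The stated 271 per arm is reproduced, with the 5% acting as infants removed from the analysed sample.

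**2. Effect of analysing survivors only.** Let p be the reintubation risk among all randomised infants in an arm, d the risk of death after randomisation, and f the share of those deaths that followed a reintubation. Then

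- survivor-only risk = (p − f×d) / (1 − d)
- risk of reintubation or death, all randomised = p + (1 − f)×d

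The value p = 16% comes from section 7.3.1 and is applied to both arms, so there is no true difference. The death risks, 3% in arm A and 8% in arm B, are **assumptions**; on 271 infants they are about 8 and 22 deaths. The plan gives no death rate for the trial window. The value of f is unknown, so the full range is shown.

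| f | Survivors only, A vs B | B minus A (points) | Reintubation or death, A vs B |
|---|---|---|---|
| 0 | 16.5% vs 17.4% | +0.9 | 19.0% vs 24.0% |
| 0.16 | 16.0% vs 16.0% | 0 | 18.5% vs 22.7% |
| 0.5 | 15.0% vs 13.0% | −1.9 | 17.5% vs 20.0% |
| 1 | 13.4% vs 8.7% | −4.7 | 16.0% vs 16.0% |

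Worked line for f = 0.5: A = (0.16 − 0.015)/0.97 = 0.1495; B = (0.16 − 0.040)/0.92 = 0.1304.

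The break-even is f = p. Above 16%, the arm with more deaths looks better on reintubation; below it, that arm looks worse. With equal d and equal f in both arms, the difference between arms is not distorted.

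**3. Effect on numbers.** At 5% loss, 271 × 0.95 ≈ 257 per arm remain, and power for 16% versus 26% is 79.7% (pooled normal approximation). At 10% loss, 271 × 0.90 ≈ 244 remain, and power is about 78%.

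**4. Weaning time.** Kaplan-Meier and Cox can hold an infant who was never extubated, but section 8 gives no censoring or competing-event rule and the form records only a duration. Censoring at death in a Kaplan-Meier curve would treat the infant as if extubation were still possible later.

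**The case against.** The strongest reply is that a survivor-only analysis is never stated. The phrase about exclusion belongs to the consent criterion. Section 7.2 does not say that data gathered before death are discarded, and section 7.5 requires each reintubation to be recorded. This is correct. A reader might infer that reintubations before death are certain to be lost, or that infants who die must drop out of the weaning-time analysis. The documents support only that the plan permits this and does not rule it out. The gap itself stands.

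A reader might also infer that a more harmful arm will look better. The table shows that the direction depends on f, which is unknown.

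A reader might set the mortality figure in section 3.2.9 against the 5% allowance and conclude that the allowance is too small. That figure is general prognosis, not deaths between the start of weaning and 72 h after extubation, and infants must be stable to start weaning (section 7.5).

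A reader might further infer that deaths before weaning use up hospital places, since section 10.3 says "Recruitment will continue until each centre has recruited the number of participants assigned by the stratification". That sentence goes on to the 1:1 ratio, and section 7.3.3 counts 271 per protocol, so the quotas can be read as counting allocated infants. Deaths before randomisation cannot bias the arms in any case.

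Finally, section 9 commits the investigators to publishing unfavourable events, and section 10.3 says that clinical data will be in the medical record. Deaths could therefore be recovered. That softens the missing form field but supplies no analysis rule.

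**Conclusion.** The point holds as a gap that permits an outcome-linked exclusion after randomisation, not as proof that the analysis will be confined to survivors. Under the assumed 3% versus 8% deaths and equal true reintubation, the spurious difference runs from 0.9 points against the arm with more deaths to 4.7 points in its favour, compared with a design difference of 10 points. With f at one half it is 1.9 points. These sizes rest on assumed death rates, on f being the same in both arms, and on withdrawn infants leaving the analysis. If deaths are few or equal across arms, with similar f, the bias is small or absent. The loss of power, from about 80% to 78% at 10% loss, is secondary. The correction is cheap and should be made before the first infant is randomised.

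**What to change.** - **Section 7.2:** remove death from the withdrawal criteria and keep revoked consent only.
- **Section 8, population:** analyse all randomised infants in the arm assigned, and keep every reintubation recorded before death. State that an infant who dies without reintubation contributes no reintubation and appears in the deaths by arm.
- **Section 8, weaning time:** treat death before extubation as a competing event, with the infant counted as not extubated.
- **Annex 7 and reporting:** add date and time of death, and report deaths by arm.
- **Supportive analysis:** prespecify reintubation or death by 72 h after extubation, with the components shown separately. They are needed because the combined rate alone can hide a mortality difference (16.0% versus 16.0% in the last row of the table).

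The primary endpoint and sample size stay as they are. Making the composite primary would replace the stated count endpoint and undo the 16% input. If, say, 5% die and 16% of survivors are reintubated, the reference rate becomes 0.05 + 0.95×0.16 = 20.2%, and the formula in step 1 for 20.2% versus 30.2% needs about 292 evaluable infants per arm instead of 257.

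The cost is a few sentences of protocol text, one or two form fields and a little extra analysis.

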7.3 Sampling

7.3.1 Sample size

We estimated the sample size using the free online software GRANMO, and the setting for two independent proportions.

In the view of the literature published so far, the proportion of reintubation in preterm newborns that are on invasive mechanical ventilation is 16% (studies differ between 12% and 20%, an average has been made).(62,63)

Accepting an alpha risk of 0.05 and a beta risk of 0.2 in a two-sided test, **271** subjects are necessary in first group and **271** in the second to recognize as statistically significant a difference greater than or equal to 0.1 percent units. A proportion in one of both groups has been estimated to be 16%. It has been anticipated a drop-out rate of 5% (0,05).

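### Section 7.3.1 prints the target difference as 0.1 percent units, but 271 per group follows from 10 percentage points and, with that difference, only from 16% versus an unstated 26%

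*Combined protocol and SAP*

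**What the plan says.** Section 7.3.1 uses an online calculator in "the setting for two independent proportions". The error rates are given as follows: "Accepting an alpha risk of 0.05 and a beta risk of 0.2 in a two-sided test". The reference rate comes from published work on ventilated preterm newborns: "studies differ between 12% and 20%, an average has been made", which gives 16%. The section then says "A proportion in one of both groups has been estimated to be 16" per cent, without naming the group. It allows for 5% drop-out and arrives at 271 per group, chosen "to recognize as statistically significant a difference greater than or equal to 0.1 percent units". It gives no rate for the second group.

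Section 5.1 gives the direction of the main hypothesis: PSV "reduces the number of reintubations, in comparison with the use of" ACVGV. Section 6.1 words the objective neutrally, as a comparison. Section 7.3.3 carries the total of 542 into the recruitment plan.

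**The concern.** Two things in the sample-size statement cannot be taken as printed.

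- **The unit.** A difference of 0.1 percentage points around 16% is not one that 542 infants could detect.
- **The second rate.** A 10-point difference from 16% leads either to 6% or to 26%, and these need very different numbers because the variance of a proportion grows as it moves towards 50%. The plan does not say which was used. Its hypothesis is a reduction, and a reduction from the quoted published rate would lead to 6%.

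This is the plan's only power statement. As printed, an ethics committee or a reader cannot tell what effect the trial is sized for, in which arm, or with what power.

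**Working it through.** **Inputs (section 7.3.1, with 1:1 allocation from section 7.3.4).** Two-sided alpha 0.05 (z = 1.960), power 0.80 (z = 0.842), reference rate p1 = 0.16, difference d = 0.10 or, read literally, 0.001, and drop-out 5%, applied by dividing by 0.95. The plan does not give the calculator's formula, so three common ones are used:

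- Unpooled normal: n = (1.960 + 0.842)² × [p1(1−p1) + p2(1−p2)] / d², where (1.960 + 0.842)² = 7.849 before rounding.
- Pooled normal: n = {1.960 × √[2m(1−m)] + 0.842 × √[p1(1−p1) + p2(1−p2)]}² / d², where m is the mean of the two rates.
- Arcsine: n = 7.849 / {2 × [arcsin√p1 − arcsin√p2]²}.

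**Step 1: reproduce 271.** Take p2 = 0.26.

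- Unpooled: 7.849 × (0.1344 + 0.1924) / 0.01 = 256.5; /0.95 = 270.0. Rounded up to 257 first, 257/0.95 = 270.5, giving 271.
- Arcsine: 7.849 / [2 × (0.4115 − 0.5351)²] = 257.1; /0.95 = 270.6, giving 271.
- Pooled: 259.2; /0.95 = 272.9.

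So 16% versus 26% gives 270 to 273 per group and reproduces the plan's figure. A continuity-corrected version gives 294 and does not match.

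**Step 2: the fall of the same size.** Take p2 = 0.06.

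- Unpooled: 7.849 × (0.1344 + 0.0564) / 0.01 = 149.8; /0.95 = 157.6.
- Arcsine: 145.8; /0.95 = 153.5.
- Pooled: 152.5; /0.95 = 160.5.

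This is 154 to 161 per group. Continuity correction raises it to 182. None of these is near 271.

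**Step 3: the printed unit.** Take p2 = 0.159. Unpooled: 7.849 × (0.1344 + 0.1337) / 0.001² = about 2.10 million per group before drop-out. The printed unit cannot be the one used.

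**Step 4: what 271 per group can detect.** After 5% loss, 271 × 0.95 = 257 evaluable per arm. Pooled normal power is Φ{[d√257 − 1.960 × √(2m(1−m))] / √[p1(1−p1) + p2(1−p2)]}.

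| Rates compared | Difference | Power, 257 per arm |
|---|---|---|
| 16% vs 26% | 10 points, rise | 79.7% |
| 16% vs 6% | 10 points, fall | 95.4% |
| 16% vs 8% | 8 points, fall | 79.9% |

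For example, for 16% versus 6%: (0.10 × 16.03 − 1.960 × 0.4425) / 0.4368 = 1.685, and Φ(1.685) = 0.954.

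**The case against.** The strongest reply is that the plan's statement is cautious rather than false. The test is two-sided, the objective is to compare, and no arm is tied to 16%. For a 10-point difference in an unspecified direction, the rise is the harder case, so sizing for 26% gives about 80% power or more either way. This stands, and it limits the point to an unclear and misprinted statement.

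A reader might go further and infer that the trial was sized for the opposite of its hypothesis. The documents do not support that. Section 7.3.1 never says which arm has 16%; if it is PSV, 16% versus 26% runs in the hypothesised direction. Nor does the quoted 12% to 20% range settle it: 26% lies outside, but so do 6% and 8%. The case for reading 16% as the comparator rate is only that it is offered as a published average.

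A reader might also fear that an observed difference of 8 to 10 points would be misjudged against the plan. Section 8 judges results by p < 0.05 and has no 10-point threshold. With 257 per arm, even an observed 16% versus 10% gives z = 0.06 / √(2 × 0.13 × 0.87 / 257) = 2.02.

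Finally, 271 is not unique to 26% if the difference is left free: 16% versus 8% gives 257.8 by the pooled formula, and 257.8/0.95 = 271.4. That pair contradicts the stated 0.1, so it does not explain the text, but it shows that 542 can be defended for a reduction.

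**Conclusion.** The point holds as a defect of statement. The printed unit is wrong: the calculation used 10 percentage points. Given that difference, 271 comes only from 16% versus 26%, a rate that the plan neither states nor supports, and the arm with 16% is not named.

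If 16% is the ACVGV rate, which is an assumption, the hypothesised 10-point reduction needs 154 to 161 per group (308 to 322 in total). The planned 542 then gives about 95% power for that reduction and about 80% for a reduction to 8%. A reader who infers that the trial is underpowered for its hypothesis would be mistaken; for a 10-point fall from 16% the error is conservative.

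All of these figures assume 5% loss and a two-sided comparison of the proportions reintubated. They do not give the power of the t-test or the Poisson regression on the number of reintubations planned in sections 8.2 and 8.3. The arithmetic and the unit error are firm; the direction depends on the arm assumption. Severity: should fix.

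**What to change.** Keep 542 and rewrite section 7.3.1 so that it:

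1. replaces the printed difference with one in percentage points;
2. states both assumed rates by arm, in the direction of section 5.1, with the reason for each;
3. restates the power to match those rates;
4. says that the power is for a comparison of the proportions reintubated.

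An example, resting on the assumption that ACVGV has the 16% rate: with 257 evaluable infants per arm and two-sided alpha 0.05, a comparison of the proportions reintubated has about 80% power for 16% with ACVGV versus 8% with PSV, and about 95% power for 16% versus 6%. If the sponsor meant 16% for PSV, the 26% for ACVGV should be stated and justified instead.

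The cost is protocol wording only. No more infants are needed, and the recruitment plan does not change.

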7.3.2 Sample collection

As previously mentioned, the sampling method selected for the study will be a **consecutive sampling**. The choice to enter the study will be offered to the parents or legal guardians of preterm newborns that are in NICU on invasive mechanical ventilation due to NRDS.

Regarding sample collection, each hospital will be responsible for the recruitment and follow-up of its own patients.

7.3.3 Estimated time of recruitment

Recruitment will be stratified according to the proportion of preterm newborns in each hospital attends.

According to the last study on the incidence of prematurity stratified by hospital done in Catalonia (64), the 5 hospitals with the highest incidence of extremely and very preterm newborns will be included in the study. They will be named in numbers from 1 to 5.

- Hospital 1 attends 386 extreme and very preterm babies per year
- Hospital 2 attends 333 extreme and very preterm babies per year
- Hospital 3 attends 208 extreme and very preterm babies per year
- Hospital 4 attends 137 extreme and very preterm babies per year
- Hospital 5 attends 106 extreme and very preterm babies per year

The total number of extreme and very preterm babies born in these 5 hospitals per year is 1.170.

The incidence of NRDS in extremely preterm newborns is approximately 70% and the incidence in very preterm newborns is about 50% (6,44,45), so an incidence of 55% have been used to estimate the time of recruitment. (The calculation has been made with the proportion of extremely and very preterm newborns obtained from the last incidence study carried out in Catalonia (6)).

Thus, there are approximately 644 newborns with NRDS per year in these 5 hospitals.

The percentage of preterm infants born at less than 32 weeks' gestation with NRDS requiring invasive mechanical ventilation is 40%, according to the latest report of the Spanish Society of Neonatology (seNeo), carried out in 2021 (61).

So, extrapolating these data, there are 257 neonates with NRDS on invasive mechanical ventilation per year in these 5 hospitals.

To carry out the study, we need a total of 542 participants, 271 for each protocol.

So, **it will take 26 months to obtain the sample (two years and two months).**

The **final stratified recruitment** will be:

- 179 newborns from Hospital 1 (33%)
- 152 newborns from Hospital 2 (28%)
- 97 newborns from Hospital 3 (18%)
- 65 newborns from Hospital 4 (12%)
- 49 newborns from Hospital 5 (9%)

